3.2 Exclusion Criteria

1. Prior treatment with any anti-angiogenic agent (including bevacizumab).
2. Prior treatment with an anti-PD-1, anti-PD-L1, anti-PD-L2, **or** anti-CD137, or anti-cytotoxic T-lymphocyte-associated antigen-4 (CTLA-4) antibody (including ipilimumab or any other antibody or drug specifically targeting T-cell co-stimulation or checkpoint pathways).

3. Prior treatment with a monoclonal antibody within 4 weeks prior to the first dose of MK-3475 or has not recovered (i.e. \leq grade 1 or at baseline) from adverse events due to agents administered more than 4 weeks earlier.
4. Prior chemotherapy, targeted small molecule therapy, or radiation therapy within 2 weeks prior to the first dose of MK-3475 or has not recovered (i.e. \leq grade 1 or at baseline) from adverse events due to a previously administered agent.

Note: patients with \leq grade 2 neuropathy are an exception to this criterion and may qualify for the study.

Note: if a patient underwent major surgery, s/he must have recovered adequately from the toxicity and/or complications from the intervention prior to starting therapy.

5. Candidate for curative resection or urgent surgical procedure(s) needed.
6. Presence of brainstem lesions or lesions that are less than 5 mm from the hypophysis or cranial nerves.
7. Multifocal gliomas that are bilateral. Patients with unilateral multifocal gliomas may be eligible if their multifocal disease can be treated effectively and safely in a single MLA procedure. Also note that corpus callosal tumors are eligible even if they are bilateral as long as they satisfy the size and shape limits of MLA as determined by the performing neurosurgeon.
8. Presence of leptomeningeal metastases.
9. Recent (within 8 weeks) history of CNS hemorrhage unless the hemorrhage is located within the tumor that will be removed en total during surgical debulking or ablated during MLA.
10. Requires therapeutic doses of anticoagulants unless anticoagulation can be safely discontinued before surgery per standard practice (e.g. first DVT for which anticoagulation has been at least 3 months and repeat imaging demonstrates resolution of DVT) or an IVC filter can be used in place of anticoagulation. Subjects are permitted to resume anticoagulation following surgery per discretion of treating physician and/or site SOPs.
11. Received prior local therapy (stereotactic radiosurgery, brachytherapy, or carmustine wafers) to the proposed area of MLA treatment.
12. Received a live vaccine or live-attenuated vaccine within 30 days prior to the first dose of MK-3475. Administration of killed vaccines is allowed.
13. Currently receiving any other investigational agents or has participated in a study of an investigational agent or using an investigational device within 3 weeks of the first dose

of MK-3475.

14. A history of allergic reactions attributed to compounds of similar chemical or biologic composition to MK-3475 or other agents used in the study.
15. Dexamethasone > 4 mg at the time of registration.
16. Has a diagnosis of immunodeficiency or is receiving chronic systemic steroid therapy (in dosing exceeding 10 mg daily of prednisone equivalent) or any other form of immunosuppressive therapy within 7 days prior to the first dose of trial treatment (with the exception of daily dexamethasone \leq 4 mg).
17. Uncontrolled intercurrent illness including, but not limited to, ongoing or active infection, symptomatic congestive heart failure, unstable angina pectoris, cardiac arrhythmia, uncontrolled hypertension, or psychiatric illness/social situations that would limit compliance with study requirements.
18. Has an active autoimmune disease requiring systemic treatment within the past 2 years (i.e. with use of disease modifying agents, corticosteroids, or immunosuppressive drugs). Replacement therapy (e.g., thyroxine, insulin, or physiologic corticosteroid replacement therapy for adrenal or pituitary insufficiency, etc.) is not considered a form of systemic treatment.
19. Has a history of (non-infectious) pneumonitis/interstitial lung disease that required steroids or current pneumonitis/interstitial lung disease.
20. Pregnant and/or breastfeeding. Patient must have a negative serum or urine pregnancy test within 2 weeks of study entry.
21. Known history of hepatitis B (defined as hepatitis B surface antigen [HBsAg] reactive) or known active hepatitis C virus (defined as HCV RNA [qualitative] is detected) infection.
22. Known history of active TB (bacillus tuberculosis).
23. Known history of HIV (HIV 1/2 antibodies).

3.3 Inclusion of Women and Minorities

Both men and women and members of all races and ethnic groups are eligible for this trial.

4.0 REGISTRATION PROCEDURES

Patients must not start any protocol intervention prior to registration through the Siteman Cancer Center.

The following steps must be taken before registering patients to this study:

1. Confirmation of patient eligibility by Washington University
2. Registration of patient in the Siteman Cancer Center OnCore database
3. Assignment of unique patient number (UPN)

Once the patient has been entered in the Siteman Cancer Center OnCore database, the WUSM coordinator will forward verification of enrollment and the UPN via email.

4.1 Confirmation of Patient Eligibility

Confirm patient eligibility by collecting the information listed below and scanning and emailing it to the research coordinator listed in the *Siteman Cancer Center Clinical Trials Core Protocol Procedures for Secondary Sites* packet at least one business day prior to registering patient:

1. Your name and contact information (telephone number, fax number, and email address)
2. Your site PI's name, the registering MD's name, and your institution name
3. Patient's race, sex, and DOB
4. Three letters (or two letters and a dash) for the patient's initials
5. Currently approved protocol version date
6. Copy of signed consent form (patient name may be blacked out)
7. Planned date of enrollment
8. Completed eligibility checklist, signed and dated by a member of the study team
9. Copy of appropriate source documentation confirming patient eligibility

4.2 Patient Registration in the Siteman Cancer Center OnCore Database

Registrations may be submitted Monday through Friday between 8am and 5pm CT. Urgent late afternoon or early morning enrollments should be planned in advance and coordinated with the Washington University research coordinator. Registration will be confirmed by the research coordinator or his/her delegate by email within one business day. Verification of eligibility and registration should be kept in the patient chart.

All patients at all sites must be registered through the Siteman Cancer Center OnCore database at Washington University.

4.3 Assignment of UPN

Each patient will be identified with a unique patient number (UPN) for this study. All data will be recorded with this identification number on the appropriate CRFs.

4.4 Phase II Patients

As of Amendment 12, patients enrolled in the phase II portion of this trial will no longer be randomized. After registration and surgery (if applicable), these patients will undergo MLA followed by MK-3475 treatment.

5.0 TREATMENT PLAN

Patients enrolling in phase I will receive the first dose of MK-3475 will be given not more than 1 week after MLA, and it will be administered every 3 weeks +/- 4 days thereafter until progression or unacceptable toxicity.

The phase II dose will be determined during the phase I portion of this study. Patients enrolling in phase II will need to have tissue available for diagnostic purpose and for immunological monitoring. Surgical resection/debulking is per standard of care and optional for the purpose of this study and the performing neurosurgeon will determine whether each patient will undergo surgery.

All phase II patients will undergo MLA followed by MK-3475. Patients who are planning to have surgical resection/debulking will have MLA performed at least 3 weeks but not more than 6 weeks after surgical resection/debulking.

Patients who are not planning to have surgical resection/debulking will have a biopsy for tissue diagnosis and immune monitoring during MLA. If there is a patient with suspected GBM and the pathology results are not available by the time the patient is scheduled to start treatment with MK-3475, s/he will not be treated and will be removed from study. “Determined to be ineligible” will be listed as the “Reason Off Therapy” in the OnCore database. The date pathology results were reviewed and/or the date the final determination about eligibility was made will be used as the “Date Off Therapy.” Patients removed from study due to suspected GBM not being confirmed through pathology will not be included in the patient total enrolled and will be replaced.

All patients will receive their first dose of MK-3475 not more than 1 week after MLA (if applicable) or biopsy, and then every 3 weeks +/- 4 days thereafter. For patients who had surgical debulking but did not undergo MLA, MK-3475 will be started at least 3 weeks but not more than 6 weeks after surgical debulking, and then every 3 weeks +/- 4 days thereafter. Dosing of MK-3475 will continue at the dose determined by phase I until progression or unacceptable toxicity.

For all phase II patients, research blood will be drawn prior to MLA and immediately prior to the first dose of MK-3475. Subsequently, research blood will be drawn at doses 2, 4, 6, 9, 18, 36, and at the end of treatment. In addition, an optional ipsilateral cervical lymph node may be sampled by FNA prior to or at the time of surgical procedure (including surgical debulking, MLA, or biopsy) and again 6 weeks after surgery. Those patients who, in the event of surgical intervention for clinical reasons of a radiographically progressing tumor, undergo a subsequent surgical procedure (whether biopsy or resection) will have tissue collected for correlative analysis after histopathologic diagnosis of recurrent GBM.

Additionally, for patients enrolled to phase II who have surgical intervention for a radiographically progressing tumor but subsequent surgical pathology demonstrating a predominant immune-mediated reaction **with no obvious progression of tumor**, such subjects will be deemed not to have progressed and be allowed to resume assigned study treatment at a time deemed safe by the treating physician, but no later than 8 weeks from the surgery.

5.1 Premedication Administration

No premedications are required, but antiemetics may be given as per institutional practice if needed.

5.2 Agent Administration

MK-3475 will be given intravenously over the course of 30 minutes (-5 min/+10 min) on an outpatient basis. The starting dose for the phase I portion of the study is 100 mg every 3 weeks; please refer to the dose escalation schema in Section 5.4 for dosing during phase I. As determined during the phase I portion of the study, the phase II dose of MK-3475 for all patients is 200 mg. In the phase I portion of this study, MK-3475 will be given every 3 weeks starting no more than 1 week after MLA. In the phase II portion of this study, MK-3475 will be given every 3 weeks beginning no more than 1 week (+/- 3 days) after MLA.

5.3 MRI-Guided Laser Ablation

MLA is a minimally invasive laser surgery, which employs a small incision in the scalp and skull, through which a thin laser probe is inserted and guided by MR imaging to the core of the tumor mass where it delivers hyperthermic ablation from the core to the rim. The maximal temperature in the core can reach 70°C, resulting in coagulative necrosis. MLA will be performed as per standard of care. In those who have undergone a gross total resection, the MLA will be directed at treating a peritumoral margin of 0.5-1cm surrounding the resection cavity to disrupt the BBB and potentially increase access of MK-3475 to the peritumoral infiltrating glioma cells.

After initiation of anesthesia and placement of an MRI-compatible head holder, a MRI-guided navigation system is registered using preoperative MRI to define the centroid of the target lesion. After inserting the probe in the lesion and positioning the patient in the MRI scanner, the laser (1064 nm wavelength, 10-14 Watts power, pulse duration 2.2 seconds on, 1.7 seconds off) is activated and real-time thermal isodose MRI is monitored to achieve sufficient treatment (no limit to exposure duration). The NeuroBlate software provides predictive thermal dosage lines. Yellow lines for 43 °C are set for 2 min and blue lines for 43°C for 10 min to estimate ablation volume. These thermal dosage lines will be used to establish treatment duration, movement of the probe, and additional trajectories depending on the location, shape and size of the target lesion. For some patients, additional trajectories are chosen preoperatively; for other patients, additional trajectories are chosen based on thermal dosage lines of the initial trajectory. After successful ablation, the probe is removed and the wound is closed in routine fashion. Patients are generally hospitalized for one or

two days after the procedure, and monitoring will take place as described below.

Perioperative care will be consistent with current standard care for patients undergoing craniotomy or biopsy of a brain tumor. This includes either ICU or step-down unit post-operative stay. Typically, these patients are placed on perioperative steroids to reduce the risk of post-treatment edema. Also, the patients are placed on prophylactic antiepileptics (i.e. Keppra) to mitigate perioperative and post-treatment seizures. During post-operative recovery, patients have routine neurological exams per the care team. In the ICU this is on an hourly basis; in the stepdown unit this is every two hours. Additionally, post-operative labs are obtained immediately after surgery and on the following day to ensure there are no metabolic abnormalities. They are also seen in the morning and in the late afternoon by the neurosurgical team.

5.4 Phase I Dose Escalation Schema

Dose Escalation Schedule	
Dose Level	MK-3475 Dose
Level 1 (Starting Dose)	100 mg IV q3wks
Level 2	150 mg IV q3wks
Level 3	200 mg IV q3wks

A decision regarding dose escalation will not take place until all patients in the Level 1 cohort have received the post-MLA dose of MK-3475 and the Principal Investigator has been able to review all toxicities for 3 weeks after that dose.

NOTE: No later than two weeks following the completion of the first two months of treatment for the first 3 patients enrolled in this trial, interim safety data must be provided to the FDA as a formal IND submission. This submission should include a listing of all AEs of grade 2 or greater severity observed. For all AEs of grade 3 or greater severity, and for all SAEs, a narrative description of the events should be included, along with the timing of the event in relationship to study treatment, interventions, duration, and outcome.

5.5 Definition of MTD, DLT, and Dose Escalation Criteria

5.5.1 Definition of Maximum Tolerated Dose (MTD)

The maximum tolerated dose (MTD) is defined as the dose level immediately below the dose level at which 2 patients of a cohort (of 2 to 6 patients) experience dose-limiting toxicity during the first cycle. Dose escalations will proceed until the MTD has been reached or, failing that, 200 mg q3wks will be considered the MTD.

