5.5.2 Dose Limiting Toxicities (DLTs)

DLT is defined as any of the following that occur during the time frame between the first dose of MK-3475 and 3 weeks after the second dose of MK-3475 that are attributed as possibly, probably, or definitely related to the study treatment:

- Grade 2 or greater diarrhea
- Autoimmune hypophysitis
- Grade 3 or greater hepatitis
- Grade 2 or greater pneumonitis
- Significant intracranial edema requiring high-dose steroid (defined as > 16 mg/day and/or inability to taper steroids to ≤ 8 mg/day within 4 weeks due to recurrent symptoms attributable to excessive cranial edema)
- Grade 3 or greater non-hematologic toxicity
- Grade 3 or greater hematologic toxicity

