5.5.3 Dose Escalation Criteria

Dose escalations will proceed as follows after the occurrence of DLT:

Number of Patients with DLT at a Given Dose Level	Escalation Decision Rule
0 out of 3	Enter 3 patients at the next dose level
2 or 3 out of 3	Dose escalation will be stopped and 3 patients will be entered at the next lowest dose level if only 3 patients were treated previously at that dose.
1 out of 3	
 • Enter at least 3 more patients at this dose level. • If 0 of these 3 patients experience DLT, proceed to the next dose level. • If 1 or more of this group suffer DLT, then dose escalation is stopped and 3 additional patients will be entered at the next lowest dose level if only 3 patients were treated previously at that dose.
≤ 1 out of 6 at highest dose level below the maximally administered dose	This is generally the recommended phase II dose. At least 6 patients must be entered at the recommended phase II dose.

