5.6 Toxicity, Response, and DLT Evaluations

All patients who receive any treatment with MK-3475 are evaluable for toxicity. Patients are evaluated from first receiving study treatment until a 30-day follow-up after the conclusion of treatment or death.

All phase II patients are evaluable for disease response unless they come off study before any disease assessment.

A phase I patient is evaluable for DLT assessment from the time of the first dose of MK-3475 through 3 weeks following the second dose of MK-3475. Once the patient has received his/her third dose of MK-3475, s/he will no longer be evaluated for DLTs. Patients who do not incur a DLT and who receive only a single dose of MK-3475 or who do not undergo MLA should be considered not evaluable for DLT and should be replaced.

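### The MTD definition counts DLTs in the first 3-week cycle only, while the DLT definition and evaluability rule use about 6 weeks

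*Combined protocol and SAP*

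**What the plan says.** Four parts of Section 5 bear on which toxicities determine the MTD.

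- **Section 5.5.1** places the MTD one level below the dose at which 2 patients of a cohort "experience dose-limiting toxicity during the first cycle". It adds: "Dose escalations will proceed until the MTD has been reached or, failing that, 200 mg q3wks will be considered the MTD".
- **Section 5.5.2** defines a DLT as a listed, treatment-related event in "the time frame between the first dose of MK-3475 and 3 weeks after the second dose of MK-3475".
- **Section 5.5.3** drives escalation from a table headed "Number of Patients with DLT at a Given Dose Level", with no mention of a cycle, and states: "At least 6 patients must be entered at the recommended phase II dose".
- **Section 5.6** repeats the 5.5.2 window: "A phase I patient is evaluable for DLT assessment from the time of the first dose of MK-3475 through 3 weeks following the second dose". It closes the window at the next dose: "Once the patient has received his/her third dose of MK-3475, s/he will no longer be evaluated for DLTs". Patients without a DLT who "receive only a single dose of MK-3475 or who do not undergo MLA should be considered not evaluable for DLT and should be replaced".

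Section 5.4 adds a condition for Level 1 only: no escalation decision until toxicity has been reviewed for 3 weeks after the post-MLA dose. Section 5.2 records that Phase I led to 200 mg as the phase II dose.

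**The concern.** The MTD is the Phase I primary objective (Section 2.1), and the protocol gives two observation windows for it. If a cycle is one 3-week dosing interval, 5.5.1 counts DLTs in weeks 1 to 3, and 5.5.2 and 5.6 count them in weeks 1 to about 6.

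The difference has a direction. A shorter window can only lower the DLT count, so it can only leave the MTD unchanged or raise it, and 5.5.1 makes 200 mg the MTD when no level reaches the limit. Suppose two patients at 200 mg each had a DLT in week 5. On the 5.5.2 window the MTD would be 150 mg. On the literal 5.5.1 wording no level has reached the limit, and the MTD is 200 mg by default.

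Events in weeks 4 to 6 are plausible here. Section 1.4.1 gives edema as the reason for escalating dose, Section 1.2 describes imaging changes that grew 2 weeks after MLA and then lasted several weeks, and Section 6.0 notes that immune-related events may appear late.

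**Working it through.** **1. Length of a cycle.** Section 5.5 does not define the term. The inputs are the 3-week dosing interval (Section 5.0) and the treatment limits in Sections 5.9 and 5.10, which treat 35 cycles and 35 doses as the same roughly 2-year limit and 17 cycles as 12 months.

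- 24 months / 35 cycles = 2.98 weeks per cycle; conversely, 35 × 3 = 105 weeks = 24.1 months.
- 12 months / 17 cycles = 3.07 weeks per cycle; conversely, 17 × 3 = 51 weeks = 11.7 months.

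A cycle is therefore one 3-week dosing interval. Nothing redefines the first cycle as two doses.

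**2. Length of the DLT window in 5.5.2 and 5.6.** One dosing interval plus 3 weeks is 3 + 3 = 6 weeks. With the ±4-day dosing tolerance it is 5.4 to 6.6 weeks, or about two cycles.

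**3. Which window was meant.** Section 5.5.3 counts DLTs, the term that 5.5.2 defines together with its window. Section 5.6 replaces DLT-free patients who had one dose, which would make no sense if one dose completed the observation period. One DLT in 5.5.2 is failure to taper steroids within 4 weeks, which a 3-week window cannot properly accommodate. The 5.5.2 window is the evident intent, and the 5.5.1 phrase is the error.

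**4. Illustrative size.** The protocol states no operating characteristics to reproduce and no DLT rate or timing for the combination. Single-agent escalation had no DLTs (Section 1.4.1), but that does not cover MLA. The rates below are assumptions.

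For a six-patient cohort, P(at most 1 DLT) = (1−p)^6 + 6p(1−p)^5. Let p6 be the 6-week rate. The 3-week rate is p3 = 1 − √(1−p6) under a constant hazard, or p3 = 0.75 × p6 if three-quarters of DLTs occur by week 3. Because the windows are nested, the difference is the probability of meeting the limit on 3 weeks but not on 6. Differences are from unrounded values.

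| p6 | P, 6 weeks | p3, constant hazard | P, 3 weeks | Difference | p3, 75% early | P, 3 weeks | Difference |
|---|---|---|---|---|---|---|---|
| 0.05 | 0.967 | 0.025 | 0.991 | 0.024 | 0.0375 | 0.981 | 0.014 |
| 0.10 | 0.886 | 0.051 | 0.966 | 0.080 | 0.075 | 0.931 | 0.045 |
| 0.20 | 0.655 | 0.106 | 0.875 | 0.219 | 0.150 | 0.776 | 0.121 |
| 0.30 | 0.420 | 0.163 | 0.745 | 0.325 | 0.225 | 0.594 | 0.174 |
| 0.40 | 0.233 | 0.225 | 0.593 | 0.360 | 0.300 | 0.420 | 0.187 |

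**5. The same question under the sequential 3+3 rule.** The probability of stopping at a level is 1 − [(1−p)^3 + 3p(1−p)^2 × (1−p)^3]. For p6 = 20/30/40/50% with constant hazard, this is 29/51/69/83% on 6 weeks and 10/21/35/49% on 3 weeks, a gap of about 19/29/34/34 percentage points. That is slightly smaller than the six-patient figures at 20 to 40% and has the same pattern.

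**The case against.** The strongest reply is that the rest of the protocol already settles the matter. DLT is a defined term that carries its own window, 5.6 repeats it, 5.5.3 counts by it, and the single-dose replacement rule means a cohort cannot be cleared on one cycle. On this view the 5.5.1 phrase is a leftover that nobody would apply. That is a fair account of intent, but it does not make the text right. Either the phrase restricts the defined window, which is the contradiction, or it does nothing and should be removed. Section 5.4 also uses a 3-week review, so the short period is not confined to one phrase. That review is only a minimum for Level 1, however, and does not permit escalation ahead of 5.5.3 and 5.6.

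The 3-week cycle is an inference, drawn from treatment limits that Section 5.9 associates with Amendment 13. That is so, but both ratios in Section 5.9 and the dosing interval give the same answer.

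Phase I is over, and later toxicity was reviewed anyway: Section 13.0 requires review at least monthly or before each escalation, and Section 5.4 requires a safety submission to the FDA after the first 3 patients complete two months of treatment. Harm needs both that the 3-week window was used and that DLTs fell in weeks 4 to 6, and the documents show neither. This stands and limits the consequence to how the Phase I result is defined and reported.

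The rates are assumed, and the large figures come from the 20 to 40% rows. This also stands: at rates of 10% or less the effect is at most 8%.

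**Conclusion.** The inconsistency is real. The MTD definition in 5.5.1 uses about half the observation window that 5.5.2 and 5.6 use for the events it counts. It is a contradiction in the wording of a decision rule; the 3+3 design with a window of about 6 weeks is not in question.

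Any effect runs toward 200 mg. Its size is conditional: for assumed 6-week DLT rates of 5 to 40%, between 1% and 36% of six-patient cohorts would meet the limit only because the shorter window was used. These figures rest on assumed rates and timing, but the conclusion that the text conflicts does not.

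The documents give no reason to think 200 mg was wrongly chosen. The phase II PFS endpoint and its power are unaffected. What remains open is which window the Phase I primary result was, and will be, reported on. The point should be corrected, but it does not threaten the trial.

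**What to change.** In 5.5.1, replace the reference to the first cycle with a reference to the DLT window defined in 5.5.2, and word the Level 1 review in 5.4 to match. Report the Phase I MTD on the 5.5.2 window and name that window.

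If the 200 mg decision was made on the 5.5.2 window, one sentence in the report saying so is enough. If it was made on the 3-week window, re-tabulate DLTs by dose level on the 5.5.2 window and state whether 200 mg still meets the MTD definition.

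The cost is negligible: a phrase in 5.5.1, a few words in 5.4 and a sentence in the report. A re-tabulation would need no new data. Section 7.0 tracks adverse events to 30 days after the last treatment, which covers the 21 days after dose 2 (events clearly due to MLA or surgery and unrelated to MK-3475 are not recorded). Section 13.0 already requires DLT counts by cohort in the safety monitoring report.
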